## **11) Withdrawal of Subjects**

Subjects (patients and family members) may withdraw at any time. If they withdraw from the study, they will be given the option of having their records destroyed.

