## 8) Data and/or Specimen Management and Confidentiality

REDCap will be used to collect outcomes data. Procedures for maintenance and confidentiality include 1) assigning each participant a unique identifier, 2) data collected will be labeled using the unique identifier and will be stored separately from the key linking personal information (e.g. name, date of birth, address, phone number) and identifiers, 3) data will be kept on a secure server that is only accessible to research staff, 4) at the conclusion of the study, the key linking identifiers and personal information will be destroyed, 5) all research personnel in the U.S. who have access to the patient data will receive training on conducting human research (e.g. NIH online course) – all investigators in Vietnam will participate in the local equivalent of this training.

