## 9) Data and/or Specimen Banking

- a) Will the data or specimens ever be used by you or other researchers to answer a different research aim that is not included in this study?  
 Yes - Complete the remainder of Section 9.  
 No - Do not complete Section 9. Go to section 10.
- b) What will be banked for future use?  
 De-identified data/specimens. Banked data/specimens cannot be linked to an individual.  
 Identifiable data/specimens – Banked data/specimens will include identifying information.  
 Coded data/specimens – Banked data/specimens will be stripped of identifiers and assigned a code. A key will be maintained that links the identifiers to the data/specimens.  
 Contact information will be banked for future research opportunities.
- c) Where will the data/specimens be banked?  
Computer files are password protected, and data are maintained on a secure firewall-protected network of the UC Davis Health System, REDCap.
- d) How long will the data/specimens be banked?  
After the study, the key linking personal identifiers to the survey data will be destroyed. De-identified data will be kept indefinitely.
- e) Who will have access to the banked data/specimens?  
Only select researchers involved in the project will have access to these data. Only de-identified data will be shared to other researchers who wish to access banked data.

PROTOCOL TITLE: Cluster Randomized Controlled Trial to Test the Efficacy of a Psychosocial Intervention (REACH VN) to Support Alzheimer's Family Caregivers in Vietnam

f) Describe the procedures to release data/specimens. Include the process to request a release, approvals required for release, who can obtain data/specimens, and the data/specimens to be provided.

- Recipient investigators who wish to access banked data will need to contact PIs ([name] and [name]) for an inquiry.
- If PIs agree for accessing banked data, the following approval steps will be taken:
  - + Recipient investigators will submit a proposal to PIs with the following information:
    - Title
    - Recipient PI's contact information and team members/co-authors
    - Introduction
    - Research questions
    - Data variables
    - Analysis plan
    - References
  - + Recipient investigators will submit an IRB approval letter from their local institution.
  - + PIs will submit the UC Davis Data Use Agreement request to UC Davis Innovation Access for recipient investigators to complete the Data Use Agreement Form.

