Study Title: Cluster Randomized Controlled Trial to Test the Efficacy of a Psychosocial Intervention (REACH VN) to Support Alzheimer's Family Caregivers in Vietnam

NCT#: NCT04542317

Document Date: October 15, 2020

Document Type: Statistical Analysis Plan

Statistical Analysis Plan

Intervention and control arms will be compared at baseline on caregiver characteristics, people with ADRD characteristics, and caregiving context using two-sample t-tests for continuous variables and chi-squared tests for categorical variables. The Wilcoxon rank-sum test or Fisher's exact test will be used instead when parametric assumptions are violated. For primary and secondary outcomes, the assessment of intervention effects will be based on intent-to-treat analyses. The 3-month and 6-month assessments will be used as outcomes, while the baseline assessment will be used as a covariate in a mixed-effects regression model. A random intercept for participants nested within communes will be included to account for the correlation among assessments from the same participant, as well as participants belonging to the same commune.

Both unadjusted models and those adjusted for caregiver characteristics (e.g., age, gender, and relationship to people with ADRD) and people with ADRD characteristics (e.g., age, gender, dementia severity, and NPI-Q severity score) will be reported. These covariates are chosen because they are either basic sociodemographic characteristics or variables shown in prior studies to be associated with caregiver psychological stress and burden. Contrasts will be defined to estimate the difference between intervention arms at 3 and 6 months and will be tested using a Wald test. For ease of presentation, primary and secondary outcomes will be z-scored using the baseline mean and standard deviation (SD) in the group. Therefore, differences will be presented in SD units. All analyses will be conducted using SAS software, version 9.4, and a p-value less than 0.025 will be considered significant.

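### Does offering withdrawn subjects destruction of their records undermine the intent-to-treat analysis?

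*Protocol*

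**What the plan says.** Section 11 of the protocol opens the option to both members of the dyad and sets no time limit: "Subjects (patients and family members) may withdraw at any time". It continues: "If they withdraw from the study, they will be given the option of having their records destroyed". It does not say whether this means identifiers, coded questionnaire data, adverse-event forms or all of these.

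Section 8 separates coded data from identity: "data collected will be labeled using the unique identifier and will be stored separately from the key linking personal information". It adds that "at the conclusion of the study, the key linking identifiers and personal information will be destroyed". Section 9, answering how long banked data are held, says: "De-identified data will be kept indefinitely".

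For primary and secondary outcomes the SAP states that "the assessment of intervention effects will be based on intent-to-treat analyses". On the model it says: "The 3-month and 6-month assessments will be used as outcomes, while the baseline assessment will be used as a covariate". Its adjusted models also use "people with ADRD characteristics (e.g., age, gender, dementia severity, and NPI-Q severity score"). The SAP does not mention withdrawal, destroyed records or missing data.

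**The concern.** Read broadly, section 11 allows randomised data to be removed after they have been collected. Ordinary dropout after month 3 leaves a baseline value and a 3-month score, and the mixed model uses both. Destruction would remove both, with no later recovery and no baseline left for imputation.

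A second route runs through the older adult. If that person withdraws and has records destroyed, a caregiver who stays could lose the dementia-severity and NPI-Q covariates and so fall out of the adjusted model.

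The loss need not be random. Section 12 of the protocol names distress and worry about confidentiality as risks of the intervention, and distress is a primary outcome. Under section 7 the intervention arm has 3 to 6 sessions, some of them recorded, against one session in the control arm. Requests could therefore differ by arm and relate to outcome. No count of requests by arm is planned, and section 11 does not exempt safety forms.

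**Working it through.** **Do the passages conflict?** Section 9's retention sentence concerns data banked after the study. It can be read as covering whatever is left once individual requests have been met, so it does not contradict section 11. Section 12 speaks of leaving the intervention and section 11 of leaving the study, and destruction attaches only to the second. A caregiver who merely stops sessions is not offered it, although continued assessment of that caregiver is not spelled out.

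**Who can be affected in the model?**

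- Leaves before month 3: there is no outcome row either way. Only baseline data are lost, which enter the arm comparison and the z-scoring.
- Leaves after month 3 and asks for destruction: the 3-month row is lost.
- Completes both assessments: affected only if the caregiver later withdraws and asks.
- Caregiver stays but the older adult's records are destroyed: affected in the adjusted model only. The SAP also reports unadjusted models.

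**Size of the shift.** The documents give no rate or effect to reproduce. The arm size of 175 is from protocol section 4. Assumed inputs are *k*, the number of caregivers in one arm whose 3-month score is destroyed, and *g*, the baseline-adjusted gap in SD units between their mean and the full arm mean. Removing them moves the arm mean, and so the 3-month contrast, by

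shift = *k* × *g* / (175 − *k*).

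| *k* | *g* | Shift at month 3 (SD) |
|---|---|---|
| 1 | 0.25 | 0.25/174 = 0.0014 |
| 1 | 0.5 | 0.5/174 = 0.0029 |
| 1 | 0.8 | 0.8/174 = 0.0046 |
| 2 | 0.5 | 1.0/173 = 0.0058 |
| 5 | 0.5 | 2.5/170 = 0.0147 |
| 9 | 0.5 | 4.5/166 = 0.0271 |

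With *g* = 0.5, the cases *k* = 2, 5 and 9 are about 1%, 3% and 5% of an arm.

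**Yardstick.** Assume an ICC of 0.05 and a correlation of 0.5 between baseline and follow-up. The variance left after baseline adjustment is 1 − 0.5² = 0.75, of which 0.05 lies between communes and 0.70 within them. With 175 caregivers in about 21 communes per arm (protocol section 7),

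SE = √[2 × (0.70/175 + 0.05/21)] = √[2 × (0.00400 + 0.00238)] = √0.01276 ≈ 0.113 SD.

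As a share of the SE:

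- *k* = 1: 0.0014/0.113 ≈ 1% to 0.0046/0.113 ≈ 4%
- *k* = 2: 0.0058/0.113 ≈ 5%
- *k* = 5: 0.0147/0.113 ≈ 13%
- *k* = 9: 0.0271/0.113 ≈ 24%

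**Check in the planned model.** The SAP model was simulated with 350 caregivers in 42 communes, the same assumptions, and a residual correlation of 0.6 between months 3 and 6. Fits with the leavers' 3-month rows kept and removed differed as follows.

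| *k*, intervention arm | Month 3 (SD) | Month 6 (SD) |
|---|---|---|
| 2 | 0.007 | 0.004 |
| 5 | 0.013 | 0.008 |
| 9 | 0.026 | 0.015 |

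Nine in the control arm gave 0.025 and 0.015 SD with the opposite sign. Equal loss in both arms, with the same gap, cancels to about zero.

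**Precision.** If 5% of each arm were lost, 166 per arm would remain. Before any allowance for clustering, the SE would rise by √(175/166) − 1 ≈ 2.7%.

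**The case for a change.** The best case for acting does not rest on a large bias. A destroyed score cannot be restored, whereas a definition of records, an exemption for coded data and safety forms, and a log of requests by arm would be short to write. Coded data are already held apart from the key, so early destruction of the key entry could protect privacy while keeping the randomised data.

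Part of this stands. Section 11 is undefined, the loss would be permanent, and nothing in the text protects an adverse-event form not yet reported onward.

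The rest is weaker.

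- **Visibility of the loss.** Destruction does not erase the number allocated. Randomised minus analysed, by arm, stays reportable, and a simple tipping-point analysis needs only those counts and assumed values.
- **Privacy.** Clusters hold 5 to 15 caregivers (protocol section 4). Coded rows carrying commune, age and relationship might be recognisable without the key, so keeping them is not plainly equivalent to erasure.
- **Cost.** Withdrawing the option needs approval from both ethics boards and a changed verbal-consent script. It would also leave earlier and later participants under different rules. The consent text is not in the review copy, so what participants are told about their records cannot be checked.
- **Safety forms.** The documents do not show that any adverse-event report would be lost.

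**Conclusion.** The wording is incomplete, but the plan does not need to change. Sections 9 and 11 of the protocol and the SAP can be followed together. A destroyed outcome is one rare form of missing outcome, and an analyst would treat and count it as such.

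Over the assumed range of one to nine caregivers in one arm, the 3-month contrast shifts by about 0.001 to 0.027 SD against an SE of about 0.11 SD. Even the upper end, about a quarter of an SE, needs nine caregivers in one arm to give a 3-month score, leave, all ask for destruction, differ by 0.5 SD on average, and have no counterpart in the other arm. The values of *k*, *g*, the ICC and the correlations are all assumptions, because the documents give no rates. The sign cannot be known.

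Whether participants may have everything erased is an ethical trade-off that the protocol has settled in their favour, and reasonably so for a minimal-risk study with verbal consent. Defining records and reporting requests by arm would be useful housekeeping. It would record detail that sensible conduct and reporting can supply, and would not alter the trial's conclusion.

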## **12) Risks to Subjects**

The main risks associated with this study: 1) discomfort or mild distress because of the intervention, 2) inconvenience because of the need to fill out the study questionnaires, and 3) loss of confidentiality. These risks are similar to the risk of undergoing routine assessments in healthcare clinics in Vietnam. Specific steps are being taken to address each category of risk.

*Discomfort due to the intervention:* Even though this study builds on evidence-based strategies for support of family caregivers, subjects may experience discomfort or mild distress when discussing their caregiving experience or because of concerns about confidentiality. These risks will be minimized in several ways. Interventionists will be trained to enhance their skills to be empathetic listeners to create an emotionally comfortable environment for family caregivers. Interventionist will be trained to remind patients that they are not required to answer any questions and can withdraw from the intervention at any time or choose to end a session early. For extreme situations of emotional stress (e.g., involving threats of self-harm), interventionists will have an established protocol in emergency situations to minimize risk of harm.

PROTOCOL TITLE: Cluster Randomized Controlled Trial to Test the Efficacy of a Psychosocial Intervention (REACH VN) to Support Alzheimer's Family Caregivers in Vietnam

*Inconvenience due to questionnaires:* To address the inconvenience associate with completing study questionnaires, we will give subjects the option of completing these in the home or by phone. In addition, during the consent process, participants will be advised that they can choose not to answer any questions that make them feel uncomfortable. Risks to subjects are minimal for several reasons.

*Loss of confidentiality:* Steps will also be taken to protect against risk regarding loss of confidentiality which is particularly important in Vietnam where staff may not be as familiar with research and the importance of confidentiality. All staff will receive training and education about the importance of maintaining confidentiality as a core aspect of the research to minimize of risk. When conducting interviews, staff will try to maintain a private space and discuss the participant's level of comfort in talking to the interviewer or interventionist if others are within earshot. In the consent process, participants will be informed about loss of confidentiality as a risk and the precautions being taken to minimize this.

*Other:* This is a behavioral intervention and does not involve drug treatment. In prior studies conducted with multi-cultural populations in the United States, there have not been any serious adverse side events attributable to the intervention (personal communication with one of the PIs of a large-scale national study). Similarly, in a pilot study there were no serious adverse events related to this intervention. It is also possible that elder/abuse or neglect may be detected during the study and require intervention. A protocol for handling cases of abuse/neglect according to local norms/resources has been developed in collaboration with our colleagues in Vietnam.

### **13) Potential Benefits to Subjects**

There are several potential direct benefits to subjects. Subjects may experience an increase in their knowledge and skills because of the intervention. In addition, caregivers will learn stress reduction techniques that may help reduce caregiving-related distress. Older adults participating in screening will be given the option of having information about their cognitive testing be provided to their primary care physician.

Participants will receive \$4 at the end of the screening session and \$8 at the end of each study visit (including intervention sessions and visits for administration of assessments).

### **14) Multi-Site Research**

This is a single-site, multiple PI, international study with [name] as the lead investigator. Approval for the study will be obtained by both the UC Davis IRB and the Vietnam National Geriatric Hospital IRB. [name] will be responsible for coordinating with the international site to ensure that the most current version of the protocol and consent document are used. He will work with the PI at the Vietnam National Geriatric Hospital to ensure that 1) Participating sites will

PROTOCOL TITLE: Cluster Randomized Controlled Trial to Test the Efficacy of a Psychosocial Intervention (REACH VN) to Support Alzheimer's Family Caregivers in Vietnam

safeguard data as required by local information security policies, 2) All local site investigators conduct the study appropriately, and 3) All non-compliance with the study protocol or applicable requirements will be reported in accordance with local policy.

**15) Community-Based Participatory Research**

NA

**16) Provisions to Protect the Privacy Interests of Subjects**

Describe the steps that will be taken to protect subjects' privacy interests.

"Privacy interest" refers to a person's desire to place limits on whom they interact or whom they provide personal information.

Describe what steps you will take to make the subjects feel at ease with the research situation in terms of the questions being asked and the procedures being performed. "At ease" does not refer to physical discomfort, but the sense of intrusiveness a subject might experience in response to questions, examinations, and procedures.

Indicate how the research team is permitted to access any sources of information about the subjects.

**17) Compensation for Research-Related Injury**

NA – minimal risk study

**18) Economic Burden to Subjects**

There are no costs that subjects may be responsible for because of participation in the research.

**19) Drugs or Devices**

NA

**20) [ClinicalTrials.gov](#) Registration**

**Section 1: NIH Funded Studies**

If yes to BOTH, the study must be registered on Clinicaltrials.gov.

Yes	
	This study is funded by the NIH . (If this study is not funded by NIH, go to Section 2.)
	One or more human subjects will be prospectively assigned to one or more interventions (which may include placebo or other control) to evaluate the effects of those interventions on health-related biomedical or behavioral outcomes.

**Section 2: Studies subject to FDA jurisdiction**

If yes to ANY the study must be registered on Clinicaltrials.gov.

PROTOCOL TITLE: Cluster Randomized Controlled Trial to Test the Efficacy of a Psychosocial Intervention (REACH VN) to Support Alzheimer's Family Caregivers in Vietnam

Yes	
	This is a prospective clinical study of health outcomes in human subjects that compares an intervention with an FDA-regulated device against a control. This is not a small clinical trial to determine the feasibility of a device, or a clinical trial to test prototype devices where the primary outcome measure relates to feasibility and not to health outcomes.
	This is a pediatric postmarket surveillance of a device as required under section 522 of the Federal Food, Drug, and Cosmetic Act.
	This is a controlled clinical investigation, other than a phase I clinical investigation, of a drug subject to section 505 of the Federal Food, Drug, and Cosmetic Act or to section 351 of the Public Health Service Act.

To view a flowchart describing applicable clinical trials subject to FDA jurisdiction click [here](#).

### Section 3: Publishing the results

If yes to BOTH the study must be registered on Clinicaltrials.gov.

Yes	
	This study prospectively assigns people or a group of people to an intervention, with or without concurrent comparison or control groups, to study the cause-and-effect relationship between a health-related intervention and a health outcome.
	The PI has access to and control over all the data from the clinical trial and has the right to publish the results of the trial and plans to publish the results in a journal that follows the ICMJE recommendations .

This requirement includes studies of behavioral interventions.

### Section 4: Registration on Clinicaltrials.gov is not required

Yes	
	I have read sections 1-3 above and registration on clinicaltrials.gov is not required for this research.

## 21) Criteria for 10 Year Approval

If yes to all items below this research may qualify for a 10-year approval period.

Yes	
	This research involves no more than minimal risk.
	This research does not receive any federal or state government funding or funding from a private funder who requires annual review per contract.
	This research is not subject to FDA jurisdiction.
	This research does not include prisoners as participants.

PROTOCOL TITLE: Cluster Randomized Controlled Trial to Test the Efficacy of a Psychosocial Intervention (REACH VN) to Support Alzheimer's Family Caregivers in Vietnam

	This research is not subject to SCRO oversight.
	This research is not subject to oversight by the Research Advisory Panel of California (RAP of C).
	This research does not involve identifiable information held by the State of California Department or Agency
	No personnel involved in the design, conduct, or reporting of this research have a new unreported related financial interest (RFI) in this study.

Study Title: Cluster Randomized Controlled Trial to Test the Efficacy of a Psychosocial Intervention (REACH VN) to Support Alzheimer's Family Caregivers in Vietnam

NCT#: NCT04542317

Document Date: October 15, 2020

Document Type: Statistical Analysis Plan

Statistical Analysis Plan

Intervention and control arms will be compared at baseline on caregiver characteristics, people with ADRD characteristics, and caregiving context using two-sample t-tests for continuous variables and chi-squared tests for categorical variables. The Wilcoxon rank-sum test or Fisher's exact test will be used instead when parametric assumptions are violated. For primary and secondary outcomes, the assessment of intervention effects will be based on intent-to-treat analyses. The 3-month and 6-month assessments will be used as outcomes, while the baseline assessment will be used as a covariate in a mixed-effects regression model. A random intercept for participants nested within communes will be included to account for the correlation among assessments from the same participant, as well as participants belonging to the same commune.

Both unadjusted models and those adjusted for caregiver characteristics (e.g., age, gender, and relationship to people with ADRD) and people with ADRD characteristics (e.g., age, gender, dementia severity, and NPI-Q severity score) will be reported. These covariates are chosen because they are either basic sociodemographic characteristics or variables shown in prior studies to be associated with caregiver psychological stress and burden. Contrasts will be defined to estimate the difference between intervention arms at 3 and 6 months and will be tested using a Wald test. For ease of presentation, primary and secondary outcomes will be z-scored using the baseline mean and standard deviation (SD) in the group. Therefore, differences will be presented in SD units. All analyses will be conducted using SAS software, version 9.4, and a p-value less than 0.025 will be considered significant.

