## 4) Inclusion and Exclusion Criteria

To be eligible for the cluster RCT, the family member will need to be the identified adult (age 18 and above) primary caregiver (i.e., the person spending who provides the most time day-to-day providing care) to an older adult with dementia who is living in the community. In the event that the primary caregiver

**PROTOCOL TITLE: Cluster Randomized Controlled Trial to Test the Efficacy of a Psychosocial Intervention (REACH VN) to Support Alzheimer's Family Caregivers in Vietnam**

is not available to participate, an alternate family member who providing substantial (i.e., at least 4 hours/day) of care to the older adult with dementia will be eligible. Caregivers will need to score  $\geq 6$  on the Zarit Burden Inventory 4-item version. All participants will be living in designated clusters in Hai Duong, Vietnam. To be eligible, clusters will have a minimum of 5 participants and a maximum of 15 participants. Clusters will be defined as geographic areas serving local health stations.

The final sample for the cluster RCT will be 350 family caregivers of persons diagnosed with dementia (175 in the active intervention and 175 in the control group). The RCT will exclude:

- Caregivers who are unable to consent
- Individuals who are not yet adults (infants, children, teenagers)
- Prisoners

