## **7) Procedures Involved**

The study will be conducted in two districts in Hai Duong, a province located near Hanoi, Vietnam. Clusters within both districts will be defined as geographic areas served by local health clinics (commune health stations). In collaboration with commune health stations, community-based screening will be conducted to identify Alzheimer's family caregivers residing in the designated clusters who will then be invited to participate in the study. Clusters will be randomly assigned to either the intervention (approximately 21 clusters, 175 caregivers) or to the enhanced control condition (approximately 21 clusters, 175 caregivers).

Staff from the National Geriatric Hospital and Hai Duong Provincial Hospital will train local staff (e.g., village health workers) to identify persons at high risk for dementia from their caseloads, including those with a history of significant memory problems, behavioral issues and evidence of functional decline.

Research staff from local health clinics will contact potential participants by phone, provide information about the project, and invite them to participate in

**PROTOCOL TITLE: Cluster Randomized Controlled Trial to Test the Efficacy of a Psychosocial Intervention (REACH VN) to Support Alzheimer's Family Caregivers in Vietnam**

screening to determine their eligibility. Verbal consent will be obtained from the older adult and a family member prior to screening by research staff. Those who consent to participate in the screening will undergo an assessment including a brief neurological exam, bedside cognitive testing and dementia stage using standard instruments, including the Mini-Cog, NPI-Q and CDR. Once an older adult has been determined to meet criteria for dementia (i.e, CDR $\geq$ 1), we will identify the adult family member providing the most day-to-day care and invite them to participate in the study and obtain verbal consent. Because of the minimal risk of both screening and behavioral intervention, verbal consent will be obtained for both.

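### The SAP's baseline comparisons use individual-level tests although communes were randomised, so they over-flag arm differences as within-commune correlation rises

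*SAP*

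**What the plan says.** The SAP opens with the baseline comparison: "Intervention and control arms will be compared at baseline on caregiver characteristics, people with ADRD characteristics, and caregiving context". The default method named for this comparison is "using two-sample t-tests for continuous variables and chi-squared tests for categorical variables". The fallback is "The Wilcoxon rank-sum test or Fisher's exact test will be used instead when parametric assumptions are violated". Nothing in this part of the SAP mentions communes.

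The outcome model that follows is different. It has a random intercept to handle repeated assessments of one caregiver, "as well as participants belonging to the same commune". The SAP closes with one threshold: "a p-value less than 0.025 will be considered significant". It does not exempt the baseline tests and does not state sidedness.

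On the design, Protocol section 7 states "Clusters will be randomly assigned to either the intervention (approximately 21 clusters, 175 caregivers", with the same numbers for the control arm. Protocol section 4 adds that "clusters will have a minimum of 5 participants and a maximum of 15 participants".

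**The concern.** When communes are randomised, caregivers from one commune go to the same arm together. If a characteristic varies between communes (ICC above 0), the difference between arm means varies more from one randomisation to another than a test on 350 independent people assumes. Its standard error is then too small and its p-value too low. The fallback tests do not help: they relax distributional assumptions but still assume independence.

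The stake is how the baseline table is read. In a cluster trial, readers use it to judge whether recruitment or case mix differed between arms. Ordinary commune-to-commune variation could be reported as a significant difference. The SAP handles clustering for the outcomes and leaves it out of this comparison.

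**Working it through.** The documents state no ICC, design effect or false-flag rate, so there is no planned figure to reproduce. The stated counts agree with each other: 2 × 21 × 8.33 = 350.

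**Inputs**
- 21 communes and 175 caregivers per arm (Protocol section 7), so the mean commune size is 175/21 = 8.33.
- Commune size 5 to 15 (Protocol section 4).
- Level 0.025 (SAP), taken as two-sided: z = 2.2414.
- ICC: assumed, 0 to 0.10.
- No restriction on the randomisation: assumed, since none is described.

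**Commune size to use.** With unequal sizes, the relevant m is the size-weighted mean, Σmᵢ²/Σmᵢ. Equal sizes give about 8.33. For 21 communes of 5 to 15 totalling 175, the maximum comes from seven communes of 15 and fourteen of 5: (7 × 15² + 14 × 5²)/175 = 1925/175 = 11.

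**Formula.** The design effect is DE = 1 + (m − 1) × ICC. The false-flag rate is 2 × (1 − Φ(2.2414/√DE)).

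Example at ICC 0.05 and m = 8.33: DE = 1 + 7.33 × 0.05 = 1.367; 2.2414/√1.367 = 1.917; rate = 0.0552.

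| ICC | DE, m = 8.33 | Rate | DE, m = 11 | Rate |
|---|---|---|---|---|
| 0 | 1.000 | 2.50% | 1.00 | 2.50% |
| 0.01 | 1.073 | 3.05% | 1.10 | 3.26% |
| 0.02 | 1.147 | 3.63% | 1.20 | 4.07% |
| 0.05 | 1.367 | 5.52% | 1.50 | 6.72% |
| 0.10 | 1.733 | 8.87% | 2.00 | 11.30% |

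At m = 8.33 these are 1.0, 1.2, 1.45, 2.2 and 3.5 times the nominal level.

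**Simulation of each named test.** No arm difference, 21 + 21 communes of 8 or 9, 175 caregivers per arm, 20,000 runs per cell. Prevalences are assumptions.

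| Test | ICC 0 | 0.01 | 0.02 | 0.05 | 0.10 |
|---|---|---|---|---|---|
| t-test | 2.47% | 2.89% | 3.69% | 5.34% | 9.07% |
| Wilcoxon | 2.46% | 3.04% | 3.56% | 5.25% | 8.66% |
| Chi-squared, 30% prevalence | 2.50% | 2.95% | 3.52% | 5.53% | 9.11% |
| Chi-squared, 5% prevalence | 2.30% | 2.56% | 3.09% | 4.71% | 7.85% |
| Fisher, 30% prevalence | 1.88% | 2.21% | 2.63% | 4.32% | 7.58% |
| Fisher, 5% prevalence | 1.32% | 1.53% | 1.87% | 3.09% | 5.69% |

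With seven communes of 15 and fourteen of 5 per arm, the t-test gave 2.34%, 3.40%, 3.95%, 6.80% and 11.30%, in line with the m = 11 column.

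**Simulation of the remedies**, over both size patterns and all five ICCs:
- t-test on commune means: 2.38% to 2.67%.
- t-test on commune proportions: 2.35% to 2.65% at 30% prevalence; 1.24% to 2.43% at 3% to 5% prevalence.
- Linear random-intercept model (REML): 1.48% to 2.70% with t on 40 degrees of freedom; 1.92% to 3.25% with a normal Wald test.

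A logistic random-intercept model (30% prevalence, communes of 8 or 9, ICC 0, 0.02, 0.05 and 0.10, 4,000 runs each) gave 1.60% to 2.50% with t on 40 degrees of freedom and 2.10% to 3.08% with a normal Wald test.

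**The case against.** The strongest objection is that little follows from the error. The outcome model already includes communes, and the SAP attaches no action to a baseline p-value. It also justifies its covariates on other grounds: "These covariates are chosen because they are either basic sociodemographic characteristics or variables shown in prior studies". This stands, and it is why the point is minor. One caution: the SAP gives the covariate lists as examples, so they are not fully closed, although the stated reason for choosing them does not involve baseline tests.

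Further objections concern the size:

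- **The ICC is assumed.** This stands. At 0.01 to 0.02 with equal communes the excess is only 0.5 to 1.1 percentage points, and Fisher's test at 5% prevalence stays below nominal. The direction needs only an ICC above 0.
- **Randomisation may have been stratified by district.** The study covers two districts, and the Protocol describes no stratification. If it was used, the within-district ICC applies. In 8,000 simulated trials with total ICC 0.05, the stratified t-test rate was about 3.8% when half the between-commune variance lay between districts and 2.4% when all of it did, against 5.2% to 5.6% unstratified. This qualifies the figures and does not make the test suitable for the design.
- **The number of communes is approximate.** With 19 per arm, m could reach (8 × 15² + 11 × 5²)/175 = 11.9; with 23 equal communes it would be 175/23 = 7.6. The range 8.33 to 11 is for exactly 21.
- **The 0.025 level may have been meant for outcomes only.** The SAP's sentence exempts nothing. At 0.05 and m = 8.33 the rates would be 5.9%, 6.7%, 9.4% and 13.7% at ICC 0.01, 0.02, 0.05 and 0.10, so the problem remains.
- **The test-based remedies can be conservative.** This is true near ICC 0 and for rare characteristics. Descriptive reporting avoids it.

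**Conclusion.** The concern holds and is minor. For any characteristic with an ICC above 0 in the comparison actually randomised, the t, Wilcoxon and (unless the category is sparse) chi-squared tests flag differences more often than the SAP's 0.025 level. Fisher's test flags more often than it would under independence, but can remain below 0.025 at low ICC. At ICC 0 there is no inflation.

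With 21 communes per arm, a two-sided test and unrestricted randomisation, the rate per characteristic is 3.0% to 3.3% at ICC 0.01, 3.6% to 4.1% at 0.02, 5.5% to 6.7% at 0.05 and 8.9% to 11.3% at 0.10. Each range runs from equal to most unequal commune sizes. Which row applies cannot be known from the documents. The primary type I error is not affected by this choice.

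**What to change.** Amend the SAP's baseline paragraph in one of two ways:

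1. Drop the significance tests and report descriptive summaries by arm. This is the simpler option.
2. If p-values are kept, take them from t-tests on commune means or proportions, or from a commune random-intercept model suited to the variable type. For the model, use between-commune degrees of freedom (42 − 2 = 40 with 42 communes). Report sparse or multi-category variables descriptively.

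The cost is wording only; no extra data are needed and the outcome model is unchanged. Under option 2 the analysis is slightly less simple. Commune-level t-tests are conservative for rare characteristics (1.2% to 2.4% at 3% to 5% prevalence), and the random-intercept test is conservative near ICC 0 (about 1.5% to 1.6%).
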